**Early Initiation of Milk Expression in Mothers of Very Low Birth Weight Infants**

**NCT 01892085**

**1/8/2014**

## PROTOCOL

### Research Design

A randomized clinical trial with three treatment arms will be conducted to determine the efficacy of alternative timing of breast milk expression (mechanical pumping) on both short and long-term breast milk supply, and Mothers who have delivered a VLBW infant prematurely will be stratified by gestational age and then randomly assigned to one of three groups and asked to mechanically pump their breasts beginning at a specific time. Timing of lactogenesis stage II will be documented, and volume of breast milk produced will be measured for the first 6 weeks following delivery.

### Sample and Setting

180 mothers who have been hospitalized anticipating delivery of an infant less than 32 weeks' gestation and weighing less than 1500 grams will be sampled by convenience from a maternity unit at Shands Teaching Hospital, a Level III tertiary care center. With a 5% anticipated drop-out rate, the final sample will include 180 mothers. The hospital is part of the University of Florida and includes a Level III (52 bed) NICU. The hospital catchment area encompasses North Central Florida and Southern Georgia, a predominantly rural and semi-rural population. 120 VLBW infants per year are delivered with 95% of these women electing to express breast milk for their infants. In our preliminary work, all but 1 mother consented for the study.

Inclusion criteria for the mothers are: 1) at least 18 years of age, 2) English speaking , 3) stated intent to breastfeed, 4) anticipating the birth of a very low birth weight infant ( $\leq 1500$  grams) between 23-32 weeks gestation. Exclusion criteria are: 1) known illicit maternal drug use, 2) history of breast reduction or augmentation, 3) positive HIV status, 4) mother not transported to recovery by 45 minutes following delivery or 5) infant not expected to live over 2 weeks following delivery.

All infants born to mothers will be included in the sample (see Targeted Enrollment Table, for Infants). Mothers delivering twins will be included since milk volume in pump dependent mothers of multiple births have been shown to be similar to mothers delivering singletons (Bishara, Dunn, Merko, & Darling, 2009). Mothers will not be approached if they have received pain medicine within the last 4 hours. Their mental and physical ability to consent will be verified with the nurse caring for them.

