### Sample Size Determination / Power Analysis

The primary foci of this study are amount of breast milk expressed after initiation and time to lactogenesis II. For the continuous longitudinal outcome amount of breast milk expressed, with 60 subjects randomized to each intervention group (early, intermediate, late initiation), we will have 85% power to detect at least a 0.5 standardized (sd units) effect size between the three intervention groups [assuming 13 time points (initial expression, days 1-7, 14, 21, 28, 35, 42)]; intra-class correlation no greater than 0.5; level of significance ( $\alpha$ )=0.02, two-tailed ]. A standardized effect size of 0.49sd (Cohen's d, "moderate" effect) is equivalent to a raw effect size of 125 ml (raw scale units) for expressed breast milk (assuming pooled sd for expressed breast milk is 250, from preliminary data. For number of hours to achieve lactogenesis II assuming  $\alpha$  = 0.02 (Type I error rate), two-sided; independent sample t-test comparison of means (adjusted for multiple comparison between 3 groups); equality of variance between groups with 60 mothers per group we will have 85% power to detect a difference of 34.1 hours (effect size  $\Delta$ =0.62s;  $s$ =55.0) between the groups.

For analysis of the continuous secondary efficacy outcome measure self-efficacy, we will have 85% power to detect a difference of 0.62 s between the three groups assuming  $\alpha$  = 0.02 (Type I error rate), two sided; independent sample t-test comparison of means; equality of variance between groups accounting for multiple comparisons.

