Mothers will be visited in their hospital room by the research coordinator, PI, or a research assistant who has completed a formal lactation course approximately 24 hours after the initial breast pumping session to ensure they are successfully using the breast pump and to provide additional instruction if needed. Mothers will also have access to lactation services and nurses on the unit. There are currently 3 part time lactation specialists

Informed consent will be obtained prior to delivery. Table 1 (below) shows randomization/stratification of

employed in the hospital who provide services to all lactating mothers in the hospital. Lactation services are provided in the NICU upon request from the nurse or physician. This is congruent with all other breastfeeding mothers and those expressing milk for their infants in the NICU.

Mothers will be provided with a supply of pre-weighed and labeled milk vials in which they will place the milk following expression per standard NICU policy. During hospitalization or while visiting their infant in the NICU, mothers will have a hospital grade electric pump available for use. Upon discharge, all mothers will be provided the same hospital grade electric pump for use while their infant is in the NICU and they continue to lactate. Mothers will be asked to bring vials from all pumping sessions to the NICU, regardless of apparent results. While mothers are still hospitalized, the mother or nurse will bring the vials to the NICU following each expression, where they will be deposited in a refrigerator specified for storage of breast milk for all infants in the NICU. Once mothers go home, they will be instructed to store their vials of expressed breast milk in the refrigerator or freezer at home, and to bring vials to the NICU when visiting their infants (standard NICU policy). All breast milk will be weighed by a research assistant blinded to the group assignment of the mother. After milk is weighed, the milk will be available for infant consumption. Should breast milk be required for infant consumption prior to being weighed, the bedside registered nurse will remove the necessary breast milk with a syringe and record the exact amount of milk removed (mL of breast milk is equivalent to mg of breast milk). Mothers who continue milk expression will be reminded 3 times per week—through phone calls, texts or during visits to the NICU—to bring in their breast milk when they visit.

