Beginning 24 hours after delivery and continuing daily, mothers will be questioned (either in person or over the phone) regarding a sudden feeling of fullness in their breasts as an indicator of the onset of lactogenesis II (Appendix H). This has been a traditional method of determining the timing of lactogenesis stage II and has been shown to correlate with actual timing of this stage (Chapman, Perez-Escamilla, 2000; Perez-Escamilla & Chapman, 2000). Due to the effects of anesthesia, post op pain, and pain medication, mothers may have difficulty appreciating indicators of the onset of lactogenesis stage II, we will therefore confirm the reliability of self-report by determining whether >100mL of milk is produced per a 24-hour period (Neville, Morton, & Umemura, 2001). Since it is anticipated the onset of lactogenesis stage II will occur during the first 7 days, the number of hours post-delivery until lactogenesis stage II will be captured and recorded by research team members in the Milk Volume log.

Prior to discharge, at day 21 and 42, mothers will be asked to complete the MAACL-R. The MAACL-R is a standardized instrument with well-documented psychometric properties that assesses mood states by using positive and negative mood states scales for Anxiety, Depression, Hostility, Positive Affect and Sensation Seeking. It consists of 132 adjectives that are at or below an 8th grade reading level and takes approximately 3 minutes to complete. This test has been successfully used by the consultant for this project in lactating mothers of premature infants (Hill et al 2006; Lubin and Zuckerman, 1999). Mothers will be phoned by the research coordinator the day before the scheduled testing day to remind them to complete the test. The written test that will be completed following discharge will be provided to the mothers upon study entry. Mothers will return the test when they visit their infant and results will be hand scored and recorded on the MAACL-R Result Log by either the RA or the research coordinator. The test and grading sheet will be purchased with institutional funds upon initiation of this project.

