#### Design/Analysis Issues.

Analysis sets. For primary analyses the intent-to-treat (ITT) sample will be used comprising all randomized mothers patients. Secondary per-protocol (completer) analysis will include mothers who were compliant with protocol requirements and for whom all required measurements have been made. ITT and per-protocol analyses will be compared to test the sensitivity of our conclusions to non-adherence/attrition.

Missing data. Every attempt will be made by the study coordinator to keep mothers in the study, with the help of the student research team members and to obtain required measurements in order to ensure the completeness of the study data. To minimize potential bias due to missing observations, mothers will be contacted by phone if vials of expressed breast milk are missed, and reasons for missing data will be carefully documented. Subject participation will only be terminated due to safety reasons for mother and infant, withdrawal of consent, or loss to follow-up. Several approaches to handle missing data in the ITT analysis set will be employed. For continuous variables using a single end-of-study value (e.g., amount of milk expressed at day 42), Little and Rubin's multiple imputation methods will be used (Little & Rubin, 1997). For analyses of longitudinal outcome data, we will use longitudinal methods (e.g. mixed models) capable of dealing with missing data (Hedeker & Gibbons, 2006).

Multiple outcome variables. In order to address possible Type I errors due to the number of outcome variables, we specify the primary outcome measures a priori corresponding to the stated a priori hypothesis and maintain the alpha (significance) level at 0.02. For analysis of secondary outcome variables, we will further adjust resulting p-values using Bonferroni-type corrections for multiple outcomes. Both unadjusted and adjusted p-values will be reported.

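### The sample-size sentence starts and ends with 180 mothers despite a 5% loss, and alpha 0.02, already used up by three pairwise comparisons of one outcome, is also presented as covering the number of outcomes

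*Combined protocol and SAP*

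**What the plan says.** **Sample size.** Sample and Setting takes 180 mothers hospitalized in anticipation of delivery and continues: "With a 5% anticipated drop-out rate, the final sample will include 180 mothers". The power section works from full arms, "with 60 subjects randomized to each intervention group", and makes no allowance for loss. For time to lactogenesis II it states "we will have 85% power to detect a difference of 34.1 hours", with an SD of 55.0 hours and a two-sided alpha of 0.02. Under Design/Analysis Issues, "the intent-to-treat (ITT) sample will be used comprising all randomized mothers".

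**Timing.** The Primary Aim section says "Informed consent will be obtained prior to delivery". The Randomization section places stratification and assignment after the birth, for mothers who still meet the criteria. Potential Problems and Alternative Strategies names the interval from consent to first expression as the likeliest place to lose mothers. It also ends study eligibility for a mother who pumps outside her designated time.

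**Alpha.** The power section calls the lactogenesis II comparison "adjusted for multiple comparison between 3 groups". Analyses for Aim 1 likewise uses 0.02 for pairwise t-tests because there are several comparisons. The paragraph on multiple outcome variables gives the same 0.02 a different purpose: "In order to address possible Type I errors due to the number of outcome variables", primary outcomes are fixed in advance and alpha is held at 0.02. Further correction is planned only for secondary outcomes. There are two primary outcomes: milk volume and time to lactogenesis II.

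**The concern.** The recruitment statement is arithmetically impossible, so a reader cannot tell whether 180 counts mothers consented, randomized or followed to the end. The stated 85% power for lactogenesis II holds only if 60 mothers per arm supply that outcome.

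The alpha statement matters more. One threshold is credited with two adjustments. If 0.02 is spent on the three pairs of arms within an outcome, nothing further protects against a false positive on either of two primary outcomes. The plan runs an overall ANOVA on volume before the t-tests, but it gives no significance level for that ANOVA and does not say that the t-tests depend on it. It describes no such step for lactogenesis II. The false-positive risk for the trial's main claims therefore depends on a rule that is not written down.

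**Working it through.** **1. The plan's own power figure.** Inputs from the power section: n = 60 per arm, difference 34.1 h, SD 55.0 h (34.1/55.0 = 0.62 SD), two-sided alpha 0.02, two-sample t-test. Power comes from the noncentral t distribution with 2n − 2 degrees of freedom and noncentrality 0.62 × √(n/2). At n = 60 the noncentrality is 0.62 × √30 = 3.40 and the critical value is 2.358, giving 84.9%. The stated 85% reproduces.

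**2. The drop-out step.** 180 × 0.95 = 171, or 57 per arm. To end with 180: 180/0.95 = 189.5, so 190. A 5% loss cannot leave 180 out of 180.

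**3. Effect on lactogenesis II power if the loss follows randomization.**

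| Per arm | Power for 34.1 h, alpha 0.02 |
|---|---|
| 60 | 84.9% |
| 59 | 84.2% |
| 58 | 83.5% |
| 57 | 82.7% |

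At 57 per arm, 85% power needs 0.638 SD, or 35.1 h. The worst case is thus about 2 power points, or 1 hour (35.1 − 34.1). It is a worst case because the procedures say "Since it is anticipated the onset of lactogenesis stage II will occur during the first 7 days", so a mother lost after day 7 can still supply this outcome.

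**4. What 0.02 covers.** 0.05/3 = 0.0167, so 0.02 is roughly a three-comparison Bonferroni level. Three tests at 0.02 sum to 0.06. Simulating the three correlated pairwise t-tests with 60 per arm and no true differences gives a 5.2% chance of at least one false positive for one outcome.

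**5. Two primary outcomes.** Same simulation, with one family of three t-tests at 0.02 for each outcome and a one-way ANOVA F as the overall test. The between-outcome correlation is not in the documents and is assumed to lie between 0 and 0.7.

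| Rule | Any false primary claim (correlation 0.7 to 0) |
|---|---|
| No gate | 8.9-10.1% |
| Volume only, gated at 0.02 | 6.4-7.1% |
| Both gated at 0.05 | 7.6-8.7% |
| Both gated at 0.02 | 3.5-3.9% |
| Both gated, all tests at 0.025 | 4.4-4.9% |

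With one arm truly different on one or both outcomes, the rate is at most 4.0% under the 0.02 gate and 5.0% under the 0.025 gate. This agrees with the bounds 2 × 0.02 and 2 × 0.025.

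**6. Price of the gate.** Power to detect a 34.1 h difference between two arms when both the overall test and that pairwise test must succeed:

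| Gate | 60 per arm | 57 per arm |
|---|---|---|
| 0.025 | 78.5-84.5% | 76.0-82.2% |
| 0.02 | 75.9-82.3% | 73.2-79.8% |

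The lower figure applies when the third arm lies midway, the upper when it equals one of the other two.

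**The case against.** **On the sample size.** The best defence is that 180 simply means the number randomized. The power section and the ITT set agree with that, and mixed models and multiple imputation let mothers with partial data contribute. This stands, and it keeps the consequence small. It does not rescue the sentence, which attaches 180 to mothers sampled before delivery and gives neither a consent target nor the stage at which the 5% is lost.

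A reader might infer that 190 consents would be enough. The documents do not support that. Between consent and randomization a mother can also cease to qualify, through birth weight, gestational age, late transfer to recovery or an infant not expected to survive. These exclusions are separate from drop-out and no rate is given for them, so 190 is a minimum.

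**On alpha.** The plan does address the number of outcomes: it names the primary outcomes in advance, uses a level below 0.05 and corrects secondary outcomes further. It would therefore be too strong to say that multiplicity of outcomes is ignored. The narrower point survives, because the same 0.02 is already committed to the pairwise comparisons.

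The ANOVA placed before the t-tests could be read as a gate. If it bound both outcomes at 0.02, the error would be about 4% and there would be little to criticise. But no condition or level is stated, and that ANOVA concerns volume only.

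A reader might also take 10% as the plan's actual error rate. That is not established. The figure assumes one t-test family per outcome. If the volume tests are repeated by day, the error is higher. If they only supplement the mixed model, the t-test simulation does not describe the main volume analysis.

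**Conclusion.** Both parts hold, with different weight.

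The drop-out sentence is wrong as printed, and the effect is modest. Either at least 190 mothers must be consented, or lactogenesis II power is 82.7% at worst for 34.1 h. It does not show that the trial is seriously underpowered.

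The alpha gap is the more important part. At 0.02 the three pairwise comparisons use about 5% on one outcome, so the same 0.02 does not also cover two primary outcomes. The chance of any false primary claim is about 9-10% ungated and about 4% with both outcomes gated at 0.02. These figures are conditional on one t-test family per outcome and on the assumed correlation range; repeated by-day volume tests would add to them. The plan never states a 5% family-wise target. It is inferred only from 0.02 being close to 0.05/3.

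No firm conclusion is drawn on volume power. A time-averaged contrast over 13 points, with compound symmetry assumed at the plan's intra-class limit of 0.5, has variance factor (1 + 12 × 0.5)/13 = 0.538. It gives about 91% at 60 per arm and 90% at 57 for 0.5 SD at alpha 0.02. That does not reproduce the plan's 85%, so it is at most a sign that a 5% loss matters little for volume.

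**What to change.** **Sample and Setting, and the power section.** State 180 as the number randomized (60 per arm, ITT on all 180) and say where the 5% falls.
- Before randomization: give at least 190 as the number to consent, and note that mothers who cease to meet the criteria after consent are additional.
- After randomization: give 171 as the number expected with complete data, and state lactogenesis II power as 82.7% at worst for 34.1 h (85% for 35.1 h).

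**Design/Analysis Issues and Analyses for Aim 1.** Name one overall three-group test per primary outcome.
- Volume: one named term of the planned mixed model, for example the joint test of treatment and time-by-treatment.
- Lactogenesis II: the group comparison of mean hours on which the power section is based.

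For both outcomes, run pairwise comparisons only if that outcome's overall test is significant. Use 0.02 for both steps (at most 4% over the two outcomes), or 0.025 if 5% is the intended family-wise level (at most 5%), and state the target. Label the day 1 through 42 ANOVA and t-tests as supportive.

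**Cost.** Rewording, no new data or visits, and at least 10 more consents (190 − 180) if the loss precedes randomization. Pairwise power for 34.1 h at 60 per arm falls from 84.9% to 78.5-84.5% with the 0.025 gate, or to 75.9-82.3% with the 0.02 gate. Those ranges assume an ANOVA-type overall test and must be recomputed if the log-rank test is chosen instead.

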### Randomization

Table 1. Randomization and Stratification of Mothers

Gestational Age	Group 1 Early Expressers	Group 2 Intermediate Expressers	Group 3 Late Expressers
23-27 weeks	0-60 minutes	61-180 minutes	181-360 minutes
28-32 weeks	0-60 minutes	61-180 minutes	181-360 minutes

mothers into groups. Following the birth of an infant weighing less than 1500 grams, with a gestational age between 23-32 weeks, mothers who continue to meet inclusion criteria will be stratified according to the gestational age of the infant (23-27 weeks and 28-32 weeks). Gestational age will be determined through one of the following; 1st or 2nd trimester ultrasound or the average of the obstetric gestational age and the results of the Ballard exam. This stratification is based upon likely differences in breast milk production in mothers who deliver earlier in gestation due to decreased mammary gland development and decreased levels of prenatal hormones necessary for preparation of the breast for lactation.

Following stratification, mothers will be randomly assigned to one of three groups to begin milk expression at different time periods following delivery. Group 1 (early expressers) will begin milk expression 0-60 minutes following delivery, Group II (intermediate expressers) will begin 61-180 minutes following delivery, and Group III (late expressers) will begin 181-360 minutes following delivery. The selection of the time periods for the groups is based upon our preliminary data showing greater milk volume and earlier lactogenesis stage II in women who began milk expression within 1 hour following delivery compared to those who began milk expression 1-6 hours following delivery (Parker et al., in press).

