Prior to discharge it will be determined whether mothers are continuing to express breast milk. This will be determined by whether mothers are bringing expressed breast milk to the NICU for infant consumption. If they are no longer expressing breast milk, they will be contacted to determine whether they would be willing to participate in a 10 minute interview concerning reasons for cessation of breast milk expression and their feeling concerning cessation of lactation. If interested, an appointment will be made for the interview during a time when the mother will be present in the hospital visiting her infant and a ~~RA who is a~~ licensed registered nurse will ask the mother (5) questions (see addendum S). Should the mother find this to be a stressful topic, the interview will cease immediately and a social worker employed in the neonatal intensive care unit experienced with caring for mothers of premature infants will be immediately notified and will assess whether further services are required.

The percentage of breast milk the infant receives weekly and the percentage of breast milk the infant is receiving upon discharge (mL/kg/d for the week prior to discharge) will be collected from the medical records (Appendix J). Neonatal nurses and physicians caring for the infants will not be told of the mother's assigned group.

## Exploratory Aim 1

Exploratory Aim 1 is to examine the effect of timing of initiation of breast milk expression on infant breast milk intake (e.g., weekly percentage of breast milk the infant receives during hospitalization and amount of breast milk infant is being fed at discharge). This information will be collected from the infant's medical records.

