### **Analyses for Aim 1**

The primary efficacy outcomes are amounts of breast milk expressed over the first 7 days post-initiation; days 14, 21, 28, 35, and 42 days post-initiation and weekly, and number of days to achieve lactogenesis stage II. To examine expressed breast milk amount over time (i.e. production of breast milk immediately after initiation and subsequently, volume measured daily over the first 7 days and on days 14, 21, 28, 28, and 42 post-initiation and weekly), we will compare the longitudinal profile of milk volume expressed in the three groups over the

study period using mixed effects models (MEM) analyses. These analyses will estimate the average change in breast milk volume within each group (early vs. immediate vs. late initiation) and individual change in breast milk volume for each mother. MEM analyses allow for missing data, measurement of study subjects at different time points during the study, and time varying covariates. MEM can also take into account the effect of clustering, i.e. correlation of repeated breast milk measurements within one subject (Hedeker & Gibbons, 2006; McCulloch & Searle, 2001). The efficacy variable expressed breast milk volume (mL) will be used as the dependent variable with treatment status (early vs. intermediate vs. late initiation), time and time-by-treatment interaction and gestational group (23-27 weeks vs. 38-32 weeks) as primary independent variables. In a second step, additional covariates will be included in the models to adjust for putative predictive variables such as age, mother's weight at delivery, diagnosis of preeclampsia or diabetes, parity, birth weight, weeks of gestation, behavioral factors including skin-to-skin contact ("kangaroo care"), lactation support and mean number of pumping attempts per day. Effect modifications of covariates will be examined through inclusion of a covariate-by-treatment interaction term in the multivariable models. For example, a significant age-by-treatment interaction would suggest that the relationship between treatment and milk volume is different for older mothers compared to younger mothers. Potential key intervening variables such as behavioral factors will be further examined using mediation analysis. Further, the relationship of maternal mood with amount of breast milk will be examined by inclusion of the MAACL-R scores obtained at discharge, days 21 and 42 in the longitudinal MEM model.

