### **Analyses for Exploratory Aims**

Aim 1. Volume of breast milk at discharge will be compared via one-way ANOVA; weekly percentage of breast milk during hospitalization will be compared between the three groups using chi-square tests.

Aim 2. In a first step, unadjusted mean time to lactogenesis stage II and mean volume of breast milk over the first 6 weeks (days 1 through 42) will be compared between the four groups: early timing of initiation of expression (TIE) / 23-27 weeks of gestation, late TIE / 23-27 weeks of gestation, early TIE / 28-32 weeks of gestation, and late TIE / 28-32 weeks of gestation, using one-way ANOVA. Subsequently, post hoc pooled t-tests (Tukey's) will be used to compare time to lactogenesis stage II and volume of breast milk means pairwise for the two early and the two late TIE groups between the two degrees of prematurity (23-27 vs. 28-32 weeks) and for the early-late TIE groups within each degree of prematurity. Adjusted means will be obtained and compared between the groups using a general linear models (GLM) approach with gestational age/degree of prematurity group as the primary independent variable and time to lactogenesis stage II (or amount of breast milk expressed at days 1-7) as the dependent variable. Additional covariates will be included in the models to adjust for putative predictive variables as described above.

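### Exploratory Aim 1 tests infant intake by ANOVA and chi-square without naming the unit of analysis; if each twin is counted separately, the tests are anti-conservative.

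*Combined protocol and SAP*

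**What the plan says.** Sample and Setting puts infants as well as mothers in the sample: "All infants born to mothers will be included in the sample". It admits mothers of twins and gives a reason that concerns the mother's output: "Mothers delivering twins will be included since milk volume in pump dependent mothers of multiple births have been shown to be similar" to that of mothers of singletons.

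Randomization allocates mothers, not infants: "mothers will be randomly assigned to one of three groups".

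The Exploratory Aim 1 section defines its outcomes on the infant, from the infant's medical record: "weekly percentage of breast milk the infant receives during hospitalization and amount of breast milk infant is being fed at discharge". Table 2 lists both under infant breast milk intake. The procedures text just before that section expresses discharge intake per kilogram per day.

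Analyses for Exploratory Aims names the tests: "Volume of breast milk at discharge will be compared via one-way ANOVA; weekly percentage of breast milk during hospitalization will be compared" across the three groups by chi-square tests. It gives no unit of analysis, cluster term or covariate for this aim.

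The only clustering that the plan discusses is in the mixed model for Aim 1, for "correlation of repeated breast milk measurements within one subject". Plurality is not among the maternal factors in Table 2 or the covariates listed in Analyses for Aim 1.

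**The concern.** One-way ANOVA and the chi-square test treat every observation as independent. Two infants of one mother are not: they have the same allocation and are fed from the same supply, so their intakes are likely to be strongly correlated. If both are entered as ordinary rows, the analysis credits the trial with more information than it has. Standard errors are then too small, and a difference between timing groups is declared more often than the nominal level allows.

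The reason given for admitting twins does not settle this. It concerns how much milk a mother produces, not how infants' intakes are to be counted.

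Expected Outcomes predicts that infants in the earliest group will be given more breast milk in hospital and at discharge. Exploratory Aim 1 is the planned comparison of infant intake between groups, so its error rate matters even though the aim is exploratory. Leaving the unit open also lets it be chosen after the data are seen.

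**Working it through.** **The plan's own figure.** No sample size, power or significance level is stated for Exploratory Aim 1. The nearest figure, 85% power for time to lactogenesis II, is maternal. It reproduces: 34.1/55.0 = 0.62; 0.62 × √(60/2) = 3.396; 3.396 − 2.326 (two-sided alpha 0.02) = 1.070; power 0.858 by the normal approximation and 0.849 by the noncentral t. It says nothing about infant intake.

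**Inputs.**
- From the documents: three groups of 60 mothers, allocation by mother, twins eligible, all infants in the sample.
- Assumed: share of mothers with twins, p, 5% to 30%; within-pair correlation of intake, ρ, 0.9, with 0.5 as a lower check. The intra-class correlation of 0.5 in the power section is for 13 repeated milk-volume times within a mother and is not a twin correlation.
- Nominal level: 5% for illustration. The 0.02 level is stated for the primary outcomes.

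**Formula.** With n mothers in a group there are np pairs and N = n(1+p) infants. The variance of the group mean is (σ²/N) × [1 + 2npρ/N], so the design effect is

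DE = 1 + 2pρ/(1+p).

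For a test on 2 degrees of freedom in large samples, the true rejection rate is P(χ²₂ > critical value/DE) = α^(1/DE).

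**Worked case, p = 20%, ρ = 0.9.** DE = 1 + 0.36/1.2 = 1.30. Standard errors are too small by 1 − 1/√1.30 = 12%. The 216 infants carry the information of 216/1.30 = 166. The rejection rate is 0.05^(1/1.30) = 0.100.

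**Simulation.** 12,000 trials per setting with no treatment effect and infants analysed as independent. The chi-square test was run on a 3 × 2 table with intake split at its mean, because the plan does not say how the percentage is categorised. Results at nominal 0.05, ρ = 0.9:

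| Mothers with twins | Infants | DE | α^(1/DE) | ANOVA | Chi-square |
|---|---|---|---|---|---|
| 5% | 189 | 1.086 | 0.063 | 0.061 | 0.056 |
| 10% | 198 | 1.164 | 0.076 | 0.079 | 0.072 |
| 20% | 216 | 1.300 | 0.100 | 0.098 | 0.090 |
| 30% | 234 | 1.415 | 0.120 | 0.117 | 0.101 |

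The simulation error is about 0.002 to 0.003. The chi-square figures are lower because splitting the outcome weakens the pair correlation: (2/π) × arcsin(0.9) = 0.71. At 20% twins this gives DE = 1 + 0.4 × 0.71/1.2 = 1.24 and 0.05^(1/1.24) = 0.089, close to the simulated 0.090.

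At ρ = 0.5 the ANOVA rates are 0.058, 0.066, 0.078 and 0.090 for the four twin shares. At nominal 0.02, with 20% twins and ρ = 0.9, the rates are 0.050 (ANOVA) and 0.045 (chi-square).

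**One observation per mother.** With 180 units the simulated rates are 0.049 and 0.046 at nominal 0.05, and 0.020 and 0.018 at nominal 0.02. A mean over two twins has variance (1 + 0.9)/2 = 0.95 of a singleton's, a negligible departure from equal variance.

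**The case against.** The strongest reply is that the plan never says each twin is a row. The sentence on infants is about enrolment, and the analysis section names no unit. A reader might infer that the plan commits to counting twins separately; the text does not go that far. Volume at discharge could also mean one value per mother, and then that ANOVA has no twin problem. This stands, and it makes the point conditional. It does not remove it: the weekly percentage is plainly an infant measure, and the per-kilogram definition of discharge intake needs an infant's own weight.

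A second reply is that the size rests on two figures that the documents do not give. That also stands. At 5% twins the error is only about 6%, which is a small excess.

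A reader might also infer that, because mothers of twins are said to produce similar volumes, each twin receives about half as much as a singleton. That holds only where supply limits intake, which the documents do not show; with ample supply both twins could receive breast milk alone. Nor would a chance imbalance in twins between groups be a bias. It is ordinary covariate imbalance, and adjusting for plurality is a matter of precision.

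Finally, the aim is exploratory. Milk volume and time to lactogenesis II are measured on the mother, so nothing here touches the primary comparison.

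**Conclusion.** The point holds in conditional form. Infants, twins included, are sampled; mothers are randomised; the outcomes of Exploratory Aim 1 are measured on the infant; and the named tests assume independence with no stated unit or allowance for twins. If infants are the rows, both tests are anti-conservative in every setting examined with twins. At nominal 5% and an assumed within-pair correlation of 0.9, the type I error runs from about 6% at 5% twins to about 12% at 30% for the ANOVA, and from about 6% to 10% for the chi-square test. At 20% twins the ANOVA error is about double the nominal rate. A lower correlation shrinks the excess.

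The documents do not support saying that the tests certainly have wrong error rates. The defect they do show is an unstated unit whose natural reading gives too small a standard error. It is worth correcting, but confined to one exploratory aim.

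**What to change.** In Analyses for Exploratory Aims, name the mother as the unit for Exploratory Aim 1 and choose one route:

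- one summary per mother, the mean intake over her infants, compared between the three groups; or
- infants kept as rows in a linear mixed or GEE model clustered on mother.

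Under either route, say how the repeated weeks are handled, whether as separate weekly comparisons or in one model that allows for correlation over weeks. State also whether discharge volume is the infant's intake or the mother's output. Add plurality to the variables recorded at delivery in Table 2, include it as a covariate, and report the numbers of infants and mothers in each group.

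The cost is a few sentences of analysis text, one extra recorded field and slightly wider confidence intervals. Sample size and the primary analyses do not change.
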